4.2 Exclusion Criteria

All exclusion criteria for the study are listed below. **Unless otherwise stated, exclusion criteria apply to all phases and cohorts in the study.** Individual lists of inclusion and exclusion criteria applicable for the dose escalation phase and for each tumor type of the dose expansion phase can be found in Appendices 2.1 to 2.5.6.

A patient will be excluded from the study for any one or more of the following reasons:

1. Patients who have had a prior anti-cancer monoclonal antibody (mAb) within 4 weeks prior to study Day 1 or who has not recovered (i.e., \leq Grade 1 or at baseline) from adverse events due to agents administered more than 4 weeks earlier prior to study Day 1.
2. Patients who have had prior chemotherapy, targeted small molecule therapy, or radiation therapy within 2 weeks prior to study Day 1 or who have not recovered (i.e., \leq Grade 1 or at baseline) from adverse events due to a previously administered agent.

Note: Patients with \leq Grade 2 neuropathy or \leq Grade 2 alopecia are an exception to this criterion and may qualify for the study.

Note: If patients have received major surgery, they must have recovered adequately from the toxicity and/or complications from the intervention prior to starting therapy.

3. Patients who are currently participating and receiving study therapy or who have participated in a study of an investigational agent and received study therapy or who have used an investigational device within 4 weeks of the first dose of treatment.
4. Patients who have received prior therapy with an anti-PD-1, anti-PD-L1, anti-PD-L2, anti-CD137, or anti-Cytotoxic T-lymphocyte-associated antigen-4 (CTLA-4) antibody (including ipilimumab or any other antibody or drug specifically targeting T-cell co-stimulation or checkpoint pathways) or if the patient has previously participated in Merck MK-3475 clinical trials. (*Not applicable for various solid tumors cohort, head and neck squamous cell carcinoma check-point inhibitor experienced group*)

5. Patients with known active central nervous system (CNS) metastases and/or carcinomatous meningitis.

Note: Patients with previously treated brain metastases may participate provided they are stable (without evidence of progression by imaging (using the identical imaging modality for each assessment, either MRI or CT scan) for at least four weeks prior to the first dose of trial treatment and any neurologic symptoms have returned to baseline), have no evidence of new or enlarging brain metastases, and are not using systemic steroids for at least 7 days prior to trial treatment. This exception does not include carcinomatous meningitis which is excluded regardless of clinical stability.

6. Patients with a known additional malignancy that is progressing or requires active treatment. Exceptions include basal cell carcinoma of the skin, squamous cell carcinoma of the skin that has undergone potentially curative therapy or in situ cervical cancer.
7. Patients who have a history of allergic reactions attributed to compounds of similar chemical or biologic composition to birinapant or pembrolizumab or their constituents.
8. Patients requiring the use of anti-tumor necrosis factor (anti-TNF) therapies, such as infliximab, or patients who have received treatment with anti-TNF therapies within 5 half-lives of the drug.
9. Patients with a diagnosis of immunodeficiency or who are receiving systemic steroid therapy (in dosing exceeding 10 mg daily of prednisone equivalent) or any other form of immunosuppressive therapy within 7 days before the first dose of study drug. The use of physiologic doses of corticosteroids may be approved after consultation with the Sponsor.
10. Patients with an uncontrolled intercurrent illness including, but not limited to, symptomatic congestive heart failure, hypertension, unstable angina pectoris, cardiac arrhythmia, autoimmune or inflammatory diseases, or psychiatric illness that would limit compliance with study requirements.
11. Patients with an active autoimmune disease that has required systemic treatment in the past 2 years (i.e., with use of disease modifying agents, corticosteroids or immunosuppressive drugs). Replacement therapy (e.g., thyroxine, insulin, or physiologic corticosteroid replacement therapy for adrenal or pituitary insufficiency) is not considered a form of systemic treatment.
12. Patients who have evidence of active, non-infectious pneumonitis. Patients with a history of (non-infectious) pneumonitis that required steroids or current pneumonitis.
13. Patients with a history of interstitial lung disease
14. Patients who are pregnant or breastfeeding, or expecting to conceive or father children within the projected duration of the trial, starting with the screening visit

- through 120 days after the last dose of trial treatment. Pregnant women and men who want to conceive a child are excluded from this study because birinapant and pembrolizumab are agents with unknown potential for teratogenic or abortifacient effects in humans. Because there is an unknown risk for AEs in nursing infants secondary to treatment of the mother with birinapant and pembrolizumab, breastfeeding should be discontinued if the mother is treated on this study.
15. Patients who have a known history of Human Immunodeficiency Virus (HIV) (HIV 1/2 antibodies), or active Hepatitis B (e.g., HBsAg reactive). Patients with active Hepatitis C (e.g., HCV RNA [qualitative] is detected).
 16. Patients who have received a live-virus vaccination within 30 days of planned treatment start. Seasonal flu vaccines that do not contain live virus are permitted.
 17. Patients who have disease that is suitable for local therapy administered with curative intent.
 18. Patients who have received transfusion of blood products (including platelets or red blood cells) or administration of colony stimulating factors (including G-CSF, GM-CSF or recombinant erythropoietin) within 4 weeks prior to study Day 1.
 19. Patients who have a history or current evidence of any condition, therapy, or laboratory abnormality that might confound the results of the trial, interfere with the patient's participation for the full duration of the trial, or it is not in the best interest of the patient to participate, in the opinion of the treating investigator.
 20. Patients who have known psychiatric or substance abuse disorders that would interfere with cooperation with the requirements of the trial.
 21. Patients who have severe hypersensitivity (\geq Grade 3) to pembrolizumab and/or any of its excipients.
 22. Patients who have received anti-PD-L2, anti-CD137, or anti-Cytotoxic T-lymphocyte-associated antigen-4 (CTLA-4) antibody (including ipilimumab or any other antibody or drug specifically targeting T-cell co-stimulation or checkpoint pathways) (*Various solid tumor cohort, head and neck squamous cell carcinoma check point inhibitor experienced group only*)
 23. Patients who have previously received birinapant treatment.

4.3 Withdrawal Criteria and Procedures

In accordance with the Declaration of Helsinki (and consistent with the applicable country's acceptance), each patient is free to withdraw from the study at any time. Medivir AB reserves the right to terminate the study at any time for any reason.

The Investigator also has the right to withdraw a patient from the study in the event of any of the following:

- Confirmed disease progression (refer to [Section 9.1.5](#))

- Pregnancy or intent to become pregnant
- Occurrence of AEs or drug toxicities requiring permanent discontinuation of birinapant or pembrolizumab
- Intercurrent illness that prevents further administration of study drug
- Patient decides to withdraw consent for study participation
- General or specific changes in the patient's condition that, in the judgment of the Investigator, render the patient unacceptable for further treatment
- Protocol Violation: Study-related findings or conduct fail to meet the protocol entry criteria or the patient fails to adhere to the protocol requirements.

A patient discontinued from study participation will continue the follow-up procedures specified in [Section 6](#). All AEs will be monitored until resolution or stabilization, or if not study related, until transfer of medical responsibility to non-study medical personnel. Patients discontinuing from treatment will be assessed for possible AEs and SAEs up to 30 days after the last dose of study drug. If an AE is identified or suspected, the patient will be required to return to the clinical site, if possible, for full evaluation, regardless of causal relationship to study-drug administration.

The reason for and date of discontinuation of study-drug treatment and the reason for and date of withdrawal from the study must be recorded on the source documentation and transcribed into the case report form (CRF). If a patient withdraws consent, every attempt will be made to determine the reason. If the reason for withdrawal is an AE or a clinically significant abnormal laboratory test result, monitoring will be continued by the Investigator until the event has resolved or stabilized, until the patient is referred to the care of a health care professional, or until a determination of a cause unrelated to the study drug or study procedure is made. The specific AE or test result(s) must be recorded on the source documentation and transcribed into the CRF.

5 INVESTIGATIONAL PRODUCT AND CONCOMINANT MEDICATIONS

Investigational product (IP) refers to birinapant and pembrolizumab. Other medications consumed either before dosing or concomitantly with study drug, may be permitted or result in the patient's exclusion or discontinuation, respectively as described below (see [Section 5.5](#) and [Section 5.6](#)).

5.1 Formulation, Packaging and Labeling

Birinapant is supplied as a sterile-filled, clear, colorless-to-pale yellow, liquid solution. Birinapant will be supplied by the Sponsor in single use 10 mL amber glass vials, formulated in 50 mM citrate buffer (pH 5.0) at a concentration of 1 mg/mL containing a total fill volume of approximately 10.5 mL. Each vial is packaged in secondary packaging (carton) to further prevent the product from potential degradation on exposure to light.

Pembrolizumab is provided by the Sponsor as a solution for injection (100 mg/4 mL).

5.2 Storage, Preparation, Stability and Accounting

5.2.1 *Investigational Product Storage, Preparation and Stability*

Birinapant must be stored frozen in secondary packaging (below -10°C) in a secured area until ready to use. When ready to prepare the birinapant solution, the desired dose is to be removed from the vial, under aseptic conditions, and the contents injected into an IV bag containing 250 mL of 0.9% sodium chloride for injection USP. The prepared solution of birinapant is stable under typical in-use conditions (i.e., ambient light and temperature) for 4 hours (time of preparation through to the end of infusion). Birinapant is stable through at least 5 freeze/thaw cycles.

Pembrolizumab must be stored under refrigerated conditions at 2°C to 8°C (36°F to 46°F). Details regarding preparation of pembrolizumab can be found in the pharmacy manual.

5.2.2 *Investigational Product Accountability*

The Investigator must maintain an accurate inventory log of all investigational product received, used, returned, and destroyed. Investigational product dispensed for all patients must be recorded on the drug accountability log. Information to be documented for each dispensed vial includes:

- Patient number and initials
- Treatment cohort number
- Dose level
- Date that investigational product was dispensed
- Amount dispensed (volumes and number of vials) per patient

The investigational product accountability log and remaining investigational product inventory will be reviewed at each monitoring visit by the Sponsor's clinical monitor.

The investigational products supplied for this study are for use only in patients properly consented and enrolled into this protocol.

5.2.3 *Retention of Samples*

It will be the responsibility of the Sponsor to ensure that adequate samples of all investigational products are retained in accordance with the relevant regulatory guidelines.

5.2.4 *Investigational Product Waste Handling*

It is recommended that healthcare workers follow the institution's standard procedures for handling cytotoxic drugs during preparation and administration of study drugs. The waste generated during the preparation and administration of study drug, including materials that come into direct contact with study drug (e.g., needles, gauze, and sponges), should be disposed in accordance with applicable governmental, and institutional policies regarding the disposal of hazardous biological materials and medical waste. Although birinapant did not

exhibit any evidence of mutagenicity in the Ames assay at 10 µM and does not demonstrate significant activity in the *in vitro* micronucleus assay at concentrations up to 130 µM in either the presence or absence of S9 metabolic activation.

Handling of pembrolizumab study drug waste is detailed in the study-specific pharmacy manual.

5.3 Dose Administration

All doses of investigational product will be administered via a 30-minute (± 10 minutes) peripheral or central IV infusion. During each 21-day treatment cycle, pembrolizumab will be administered first on Day 1 as a 30-minute (± 10 minutes) infusion. Sites should make every effort to target infusion timing to be as close to 30 minutes as possible. However, given the variability of infusion pumps from site to site, a window between -5 minutes and +10 minutes is permitted (i.e., infusion time is 30 minutes -5 min/+10 min). Birinapant will be administered 30 minutes (+10 minutes) following the completion of the pembrolizumab infusion. Birinapant will be administered alone on Day 8. A week without treatment (i.e., Days 15-21) will conclude each 21-day cycle, immediately after which the treatment cycle will be repeated (i.e., with pembrolizumab on Day 1 and birinapant on Days 1 and 8). Study drugs will be administered in the arm opposite to the site of blood-sample collection.

The birinapant dose will be administered according to the dose-escalation schedule and in the dose-expansion phase of the study, according to the RP2D that will be determined in the dose escalation phase of the study.

Dose Level	Pembrolizumab + Birinapant (per 21-day cycle)
Expansion	200 mg pembrolizumab on Day 1+ birinapant at the RP2D mg/m²/week on Days 1 and 8

The dose will be prepared by the site's Pharmacy and administered using materials known to be compatible with birinapant formulation. A filter should not be used during the birinapant infusion.

The birinapant dose calculation will be based on the patient's body surface area (BSA) using the Mosteller or institutional standard formula (to be calculated to the first decimal place) determined by height and weight at Screening (see the Pharmacy Manual). If a patient's BSA is > 2.5, then 2.5 will be used to calculate the patient's study-drug dose. If the patient's body weight has changed > 10% from that used to calculate the prior BSA, the BSA will be recalculated and the dose adjusted.

Pembrolizumab will be administered as a dose of 200 mg using a 30-minute IV infusion.

The pharmacy manual contains specific instructions for the preparation of the pembrolizumab infusion and administration of infusion solution. The dosing arm will be noted and all study blood samples for collection of safety and pharmacodynamic samples must be drawn from the contralateral arm.

5.4 Dose-Limiting Toxicity and Recommended Phase 2 Dose

The inter-patient dose escalation of birinapant will be based on the number of patients that experience a DLT. A DLT is a clinically significant event attributed to birinapant, pembrolizumab, or the combination of the 2 study drugs, during the first cycle of drug therapy and is defined as follows:

Non-hematological toxicity:

- Common Toxicity Criteria for Adverse Event (CTCAE; 4.03) Grade 3 nausea, vomiting, or diarrhea despite maximal (according to treating investigator) anti-emetic or anti-diarrheal treatment and lasting > 48 hours; or Grade 4 vomiting or diarrhea;
- \geq Grade 3 other non-hematological toxicity, excluding isolated laboratory abnormalities without clinical sequelae, except for the following:
 - Prolonged (> 7 days) serum amylase or lipase elevation;
 - Prolonged (> 7 days) aspartate aminotransferase (AST) elevation;
 - Prolonged (> 7 days) alanine aminotransferase (ALT) elevation;All of which will be considered dose limiting.

Hematological toxicity:

- Grade 4 neutropenia;
- Grade \geq 3 neutropenia with fever > 38.3°C or > 38°C (> 100.9°F or > 100.4°F) for more than one hour;
- Grade \geq 3 thrombocytopenia with bleeding

Specific toxicity:

- Cytokine release syndrome (CRS); Grade 3 or 4. Furthermore, if a Grade >2 CRS occurs during the DLT period (Cycle 1), this also triggers the permanent discontinuation of all study dosing (birinapant AND pembrolizumab) with subsequent adequate care to treat the condition (see also sections 5.5.1 and 5.5.3).

If Day 8 of treatment is held due to toxicity then the event will be considered a DLT. A prolonged delay (> 2 weeks) in initiating Cycle 2 secondary to drug-related toxicity may be considered a DLT as judged by the SRC. Events related to disease progression, intercurrent illness, or concomitant medication will not constitute a DLT. Since patients are assessed for DLTs during the first cycle, dose modifications may not be performed. If a patient experiences a DLT that is deemed related to birinapant, the dose of birinapant may be restarted at a reduced level for Cycle 2 according to dose levels indicated in Table 2/[section 3](#) and the rules stated in [section 5.5](#), and the patient may remain on study.

The decisions to dose-escalate birinapant for each Dose Level are indicated in [Table 5](#) below.

Table 5 Escalation Decision Rules

Number of Patients with DLT at a Given Dose Level	Escalation-decision Rule
Zero of 3 to 6	Enter 3 to 6 patients at the next dose level.
1 out of 3 to 6	Enter up to a total of 6 patients at this dose level. 
 • If 1 of these 3 to 6 patients experiences a DLT, proceed to the next dose level, if the next highest dose has not already been declared intolerable*. • If 1 of these 3 to 6 patients experiences a DLT and the next highest dose has already been declared intolerable, enroll a minimum of 6 patients at this dose level.
≥ 2 out of 3 to 6	Dose escalation will be stopped. This dose level may be declared the maximally administered dose (highest dose administered) and may be declared intolerable. Three additional patients may be entered at the next lowest dose level if only 3 patients were treated previously at that dose.

*Defined as ≥ 2 patients from 3-6 experiencing a DLT

Once the RP2D of birinapant combined with pembrolizumab is defined, additional patients with relapsed or refractory carcinoma will be enrolled in the dose-expansion phase of the study.

During the dose-expansion phase, an independent DMC will meet at least biannually to review the complete analysis of combined observed toxicities including emerging safety issues and reported SAEs. Such meetings may result in a reappraisal of the MTD and /or RP2D. In the event that dose de-escalation is to occur the same dose levels as indicated in Table 2 / [section 3.1.1](#) should be applied.

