3.1.1 Description of Study Design Dose Escalation Phase

The dose escalation phase of this study will employ a sequential group dose-escalation design to determine the dose-limiting toxicity (DLT) and RP2D of birinapant administered in combination with pembrolizumab, both administered as a 30-minute intravenous (IV) infusion. Pembrolizumab will be administered first on Day 1. The birinapant infusion will begin 30 minutes (+10 minutes) following the completion of the pembrolizumab infusion on

Day 1. An additional dose of birinapant only will be administered on Day 8. The dose levels of birinapant and pembrolizumab are outlined in [Table 2](#).

Table 2 Dose Escalation Schedule

Dose-Escalation Schedule	
Dose Level	Pembrolizumab + Birinapant (per 21-day cycle)*
Level -1	200 mg pembrolizumab on Day 1 + birinapant 2.8 mg/m²/week on Days 1 and 8
Level 1	200 mg pembrolizumab on Day 1 + birinapant 5.6 mg/m²/week on Days 1 and 8
Level 2	200 mg pembrolizumab on Day 1 + birinapant 11 mg/m²/week on Days 1 and 8
Level 3	200 mg pembrolizumab on Day 1 + birinapant 17 mg/m²/week on Days 1 and 8
Level 4	200 mg pembrolizumab on Day 1 + birinapant 22 mg/m²/week on Days 1 and 8

*Note: A week without treatment (i.e., Days 15-21) will follow the second week of treatment, immediately after which the next 21-day cycle commences.

A minimum of 3 and up to 6 evaluable patients will be enrolled per dose level. For patients enrolled in Dose Level 1, the birinapant starting dose will be 5.6 mg/m²/week. Dose escalation of birinapant will occur in up to three steps. The Safety Review Committee (SRC) will review all the cumulative safety data up to and including completion of Day 21 for the last patient in a cohort from that treatment group prior to dose escalation. Upon review of the safety data the SRC will determine whether or not the safety data supports dose escalation to the next sequential dose level. If the first dose level (5.6 mg/m²) is deemed intolerable, defined as ≥ 2 patients from 3-6 experiencing a DLT, the SRC may decrease the starting dose of the next dosing cohort to 2.8 mg/m² (dose level -1).

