3.1.3 Safety Review Committee Dose Escalation Phase

A SRC will be involved in the conduct of the dose escalation phase of this study. The SRC will be comprised of representatives from the Sponsor and the study sites, and the SRC may recommend that the study be interrupted or terminated at any time if, in their judgment, serious or unexpected AEs of sufficient concern warrant such action. See reporting requirements ([Section 8.3](#)) for Serious AEs (SAEs). The SRC has the responsibility for monitoring the clinical study's progress and the safety of the participating patients

Following completion of a dosing level, an evaluation of the safety of that dose will be performed by the SRC (based on cumulative data to the time of SRC assessment). The SRC will review the safety, efficacy and pharmacodynamic data (when available) from all patients enrolled at each dose level to confirm any DLTs that were experienced and to make a recommendation regarding enrollment in the next dose level. Each of the 3 to 6 patients at a dose level must have completed Cycle 1 (21-day cycle) to be eligible for SRC review. On the basis of the findings, the committee will have several options:

1. Recommend escalation to the next dose level,
2. In case of unexpected or unacceptable toxicity during the dose escalation phase recommend early discontinuation of the study, or
Alter the subsequent dose as per the dose escalation criteria presented in [Section 5.4](#).

The SRC will make the decision on RP2D based on an MTD of the combination being the occurrence of greater than 2 defined grade 3 or above SAEs (for definition of DLTs see section 5.4) in the final cohort of 3 plus 3 subjects. In the absence of an MTD, the SRC will consider pharmacodynamic and PK of birinapant as applicable considering that birinapant monotherapy has been studied previously at 10 to 63 mg/m². Doses > 47 mg/m² will not be considered.

Further details on the SRC procedures are presented in the SRC-charter

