12.2 Determination of Sample Size

No formal sample size or power calculations will be performed for the dose-escalation phase of the study. A sample size of 3 to 6 patients per cohort is a feasible sample size to assess safety for dose escalation and dose-limiting toxicity. Additional patients may be needed for cohort expansion during dose escalation, for the replacement of non-evaluable patients. Only patients who do not complete the first cycle due to study drug related toxicity will be replaced.

Once the RP2D of birinapant combined with pembrolizumab is defined, additional patients with relapsed or refractory carcinoma will be enrolled in the dose-expansion phase of the study.

The dose expansion phase will comprise 4 cohorts of 26-30 patients, as follows:

- Colorectal cancer (28 patients)
- Ovarian cancer (27 patients)
- Cervical cancer (26 patients)
- Various solid tumors (30 patients, including 5 patients with each of the 6 following tumor types: (Small cell lung cancer; Cholangiocarcinoma; Gastroesophageal carcinoma; Mesothelioma; Head and Neck Squamous Cell Carcinoma (HNSCC)-checkpoint inhibitor-naïve; and HNSCC checkpoint inhibitor-experienced)

A Simon's 2-stage design (Simon 1989) will be used for each of the cohorts in colorectal cancer, ovarian cancer and cervical cancer, as outlined in Table 17. A predefined interim analysis allowing stopping each of these cohorts for futility and safety will be conducted in the first stage to limit undue exposure before further inclusion into a given cohort.

The interim analyses will be based on at least 6 and most 13 patients having completed from 9 up to 27 weeks of treatment (3 to 9 cycles) in the colorectal cancer cohort and based on at least 6 and at most 16 and 15 patients in the ovarian cancer cohort and

cervical cancer cohort, respectively. Note that one additional patient will be included in each cohort. This patient will only be included in the interim analysis in case a patient drops out in that cohort. Thus, the number of included patients in each cohort will be 27+1 (CRC), 26+1 (ovarian) and 25+1 (cervical). In all cases this extra patient will be included in the main/end analysis. If the predefined level for success in a given cohort is reached prior to the stipulated number of patients being enrolled/completed, enrollment in that cohort may be discontinued.

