12.4 Analysis Population

The following four populations will be defined for this study:

- Intent-to-Treat Population (ITT): will comprise any patient that is enrolled to the study and receives a dose of pembrolizumab and birinapant. Note that the ITT population can be considered equivalent to the Full Analysis Set population as no randomization is done in this study.
- Safety Population: will be the same as the ITT population.
- Efficacy Evaluable Population: will comprise all patients in the ITT population who have baseline and at least one post-baseline efficacy assessment, unless the patient dies or experiences an AE that results in study drug termination prior to assessment. At that point, the patient will be considered to have progressed in the absence of other data.
- Pharmacodynamic Population: The pharmacodynamic population will include all treated patients for whom pre- and post- infusion pharmacodynamic data are available.

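### The dose-escalation replacement rule in Protocol 12.2 is inverted: it replaces patients stopped in Cycle 1 by drug toxicity, who have DLTs, and bars replacement of those who leave for other reasons.

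*Protocol*

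**What the plan says.** Protocol 5.4 lists Grade 3 or 4 CRS as a DLT, and for Cycle 1 adds: "if a Grade >2 CRS occurs during the DLT period (Cycle 1), this also triggers the permanent discontinuation of all study dosing". The same section says "If Day 8 of treatment is held due to toxicity then the event will be considered a DLT". Events related to disease progression are not DLTs.

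Protocol 3.1.1 sets the size of each level: "A minimum of 3 and up to 6 evaluable patients will be enrolled per dose level". Protocol 3.1.3 says each of those 3 to 6 patients "must have completed Cycle 1 (21-day cycle) to be eligible for SRC review". It also has the SRC review data "from all patients enrolled at each dose level to confirm any DLTs that were experienced".

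Protocol 12.2 allows extra escalation patients "for the replacement of non-evaluable patients" and follows with the restriction: "Only patients who do not complete the first cycle due to study drug related toxicity will be replaced".

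Neither document defines evaluability for DLT. Protocol 12.4 opens with "The following four populations will be defined for this study" and lists ITT, safety, efficacy evaluable and pharmacodynamic. SAP 5.2 adds a pharmacokinetic population. SAP 3.3.1.1 repeats the escalation sample-size text without the replacement sentence, so it does not settle the matter.

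**The concern.** In a dose-escalation cohort, replacement exists for patients who cannot inform the DLT rate: those who leave the observation window early for reasons unrelated to the drugs. A patient who stops because of drug toxicity is the most informative patient in the cohort. Section 12.2 assigns replacement to the second kind of patient and, through its opening restriction, withholds it from the first.

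DLT counts drive escalation and inform the choice of the recommended phase 2 dose, which up to 111 expansion patients are then to receive. A replacement rule that points at the wrong patients leaves the denominator of that count unclear, and gives a reader some basis for setting aside a patient who had a DLT.

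**Working it through.** The plan states no operating characteristic for escalation, so there is no figure of its own to reproduce. The check is first a comparison of the rules, then a conditional calculation.

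**Step 1: three patients who leave Cycle 1 early**

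| Patient | 5.4: DLT? | 3.1.3: completed Cycle 1? | 12.2: replaced? | Sensible rule |
|---|---|---|---|---|
| Grade 3 or 4 CRS after the Day 1 infusions, both drugs stopped | Yes | Not if completion means dosing | Yes | Evaluable, counted, not replaced |
| Day 8 dose held for toxicity | Yes | Not if completion means dosing | Yes, on the same reading | Evaluable, counted, not replaced |
| Leaves before Day 21 for progression or withdrawal, no DLT | No | No | No | Replaced |

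In every row the 12.2 answer is the opposite of the sensible one. The third row does not depend on how DLTs are counted. That patient cannot be scored over a full window, fails the 3.1.3 condition, and is excluded from replacement. A level may enrol up to six, so the gap might be filled by enrolling a further patient within that limit, but 12.2 does not provide for it as a replacement.

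**Step 2: what would follow if replaced DLTs were not counted**

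This condition is not stated anywhere in the documents. The inputs below are assumptions:

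- p = true Cycle 1 DLT rate, taken as 0.2, 0.3 and 0.4.
- f = share of DLTs that prevent completion of Cycle 1, taken as 0.25 and 0.5.

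The DLT rate among the patients left to be scored is q = p(1 − f)/(1 − pf). With p = 0.4 and f = 0.5, q = 0.20/0.80 = 0.25. With every DLT counted, q = p.

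The escalation wording supports two readings of one DLT in three:

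- *Classic 3+3* (Protocol Table 5, expanding to six before deciding): P = (1 − q)³ + 3q(1 − q)²·(1 − q)³.
- *One DLT in three allows escalation* (Protocol 3.1.1, where enrolment at the next level proceeds): P = (1 − q)³ + 3q(1 − q)².

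For p = 0.4 with all DLTs counted, the classic rule gives 0.216 + 3(0.4)(0.36)(0.216) = 0.309. The second reading gives 0.216 + 0.432 = 0.648. With q = 0.25 they give 0.600 and 0.844.

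| p | Classic 3+3: all counted | f = 0.25 | f = 0.5 | One in three allowed: all counted | f = 0.25 | f = 0.5 |
|---|---|---|---|---|---|---|
| 0.2 | 71% | 80% | 89% | 90% | 93% | 97% |
| 0.3 | 49% | 61% | 76% | 78% | 85% | 92% |
| 0.4 | 31% | 43% | 60% | 65% | 74% | 84% |

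The direction is the same throughout: dropping these DLTs makes a level look safer. The size depends on p, f and which reading of the escalation rule is used.

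**The case against.** The strongest reply is that no section takes a DLT out of the count. Section 5.4 bases escalation on the number of patients who experience a DLT, and Table 5 counts patients with a DLT at the level. Sections 3.1.1 and 3.1.3 give the SRC the cumulative safety data and the data of all enrolled patients. Section 12.6 summarises DLT incidence for the ITT population, which includes a patient who develops CRS after receiving both drugs on Day 1. Section 12.2 is about sample size and sets no scoring rule, so adding a patient and counting the first patient's DLT are compatible. Discarding the DLT would also empty the Day 8 rule of effect.

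All of that stands. A reader might infer from 12.2 and 3.1.3 together that a patient with Grade 3 or 4 CRS falls outside the scored cohort and that DLTs are therefore lost. The documents do not support that inference. Completing Cycle 1 could also mean that 21 days have elapsed, in which case a patient followed to Day 21 after stopping dosing meets 3.1.3.

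It would likewise be wrong to assume that every DLT ends Cycle 1. Section 5.4 lets some patients with a DLT restart at a reduced dose in Cycle 2, and CRS after the Day 8 infusion comes after all Cycle 1 dosing. Finally, 3.1.3 refers to an SRC charter that is not among these documents and may define evaluability, and both the separate SRC review of the phase 2 dose and the later data monitoring committee offer further checks.

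None of this repairs the 12.2 sentence. It shows that an SRC can do the right thing, not that the protocol tells it to, and it does not help the patient who leaves for progression or withdrawal.

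**Conclusion.** The point holds as an error in the replacement rule combined with an undefined term. As written, 12.2 designates patients with drug-related Cycle 1 failures for replacement as non-evaluable, although 5.4 gives them a DLT, and it excludes from replacement the patients who lack a full DLT window. This conclusion rests on the text alone and needs no assumed rate. It may be a drafting slip for the reverse wording.

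It is not established that any DLT would go uncounted. The increases in the chance of escalation, such as 31% to 60% or 65% to 84% at p = 0.4 and f = 0.5, are illustrations. They require the replaced patient's DLT to be dropped, and they rest on assumed DLT rates and shares and on the chosen reading of the escalation rule. They show why the wording should be corrected, not what the trial will do.

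**What to change.** (a) In Protocol 12.2, replace the restriction with: *Patients who do not complete Cycle 1 for reasons other than study drug related toxicity will be replaced. A patient with a DLT is evaluable, is counted in Table 5, and is not replaced.*

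(b) In Protocol 3.1.3, change the condition for SRC review to having completed Cycle 1 or had a DLT.

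(c) Optionally, add a DLT-evaluable population to Protocol 12.4 and SAP 5.2. The minimum exposure required of patients without a DLT is the sponsor's choice.

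The cost is a protocol amendment with IRB approval (Protocol 21.1) and possibly a few additional escalation patients to replace dropouts unrelated to toxicity. No new visits or procedures are needed. For any dose level already scored, the sponsor should check whether a replaced patient had a drug-related toxicity and whether it was counted.
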